## 1 Background Information

### 1.1 Hypoparathyroidism

Hypoparathyroidism is a rare clinical syndrome that results from reduced or absent parathyroid gland function and is characterized by low serum calcium (Se-Ca) levels, elevated serum phosphorus levels, and absent or inappropriately low levels of parathyroid hormone (PTH) in circulation. Hypoparathyroidism is most often caused by inadvertent removal or destruction (i.e., radiation treatment) of the parathyroid glands, the presence of autoimmune or congenital diseases, or low blood plasma magnesium levels. The low production of PTH in hypoparathyroidism patients leads to abnormally low calcium levels in blood, and an increase of phosphorus in the blood.

PTH is secreted in response to low blood Se-Ca levels. To release more ionic calcium into the blood, PTH indirectly stimulates bone matrix turnover, enhances renal tubular calcium reabsorption, as well as intestinal calcium absorption.

Patients with hypoparathyroidism most often present with paresthesia, cramps, or tetany, but the disorder may also manifest acutely with seizures, bronchospasm, laryngospasm, or cardiac rhythm disturbances. In the postsurgical setting, the presentation can be acute with tetany, cramping, tachycardia, and altered mental status predominating. Affected individuals are most often diagnosed with low blood calcium, magnesium and PTH levels, but high phosphorus levels, and frequently show increased urinary calcium excretion, which can lead to nephrocalcinosis and kidney stones. Hyperphosphatemia can be associated with deposition of calcium-phosphate complexes in other soft tissues.

#### 1.1.1 Hypoparathyroidism standard of care

Current standard of care for hypoparathyroidism includes oral calcium carbonate supplements and active forms of vitamin D. Under restrictions, alternative treatment with once-daily injections of Parathyroid hormone (rhPTH (1-84), Natpara®) has been approved by the FDA only for patients whose calcium levels can't be controlled with calcium and vitamin D supplements.

### 1.2 Extend Biosciences' EXT608

EXT608 is under development as an extended half-life hPTH(1-34), covalently attached to a derivative of vitamin D using the D-VITYlation® technology, which results in an extended half-life and improved absorption and bioavailability of PTH, aimed at reducing the rate and/or doses of injections. For more information refer to the Investigator's Brochure (1).

The purpose of this study is to characterize the safety, tolerability, pharmacokinetic (PK), and pharmacodynamic (PD) profiles of EXT608 when administered as a single dose to healthy adult participants. EXT608 has undergone a full non-clinical testing program as recommended by the FDA and is therefore ready to be studied in humans to further its development. Data from this study are intended to identify and select pharmacologically active dose levels for subsequent dose ranging and other studies in patients with hypoparathyroidism.

### 1.3 Rationale for Dose Selection

## 2 Trial Objectives and Purpose

The purpose of this first-in-human study is to obtain initial safety, tolerability, PK, and PD information about EXT608 to facilitate optimal design of the first clinical study conducted in participants with the target indication.

### 2.1 Primary Objective

The primary objective is to characterize the safety and tolerability profile of escalating dose levels of EXT608 when administered to healthy adult participants as a single injection as assessed by:

1. Incidence, nature, and severity of adverse events (AEs) and withdrawals due to treatment emergent AEs (TEAEs) [Time Frame: Day 0 up to Day 28]
2. Frequency and severity of post-dose change from baseline in hematology, serum chemistries, urinalysis, electrocardiogram (ECG), vital signs, and physical examination (Exam) findings [Time Frame: Day 0 up to Day 28]
3. Percentage of participants with injection or infusion site reactions [Time Frame: Day 0 to Day 7]

### 2.2 Secondary Objectives

The secondary objectives are to assess:

1. Single dose PK including  $AUC_{0-24h}$ ,  $AUC_{0-48h}$ ,  $AUC_{0-28d}$ ,  $AUC_{0-\infty}$ ,  $C_{max}$ ,  $T_{max}$ ,  $T_{1/2}$ ,  $\lambda_z$ ,  $Cl/F$  and  $V_z/F$ .
2. Single dose PD by post-dose change from baseline in serum chemistries with particular attention to Se-Ca, phosphate, magnesium, and creatinine. Urinalysis will also be performed.

### 2.3 Exploratory Objectives

Furthermore, the exploratory objectives are to assess:

1. Single dose Immunogenicity by anti-drug antibodies (ADA) and any neutralizing subset (NAb),
2. Single dose effect on vitamin D metabolism by serum 25-hydroxy-vitamin D and 1,25-dihydroxy-vitamin D concentrations.

### 3 Trial Design

#### 3.1 Design Description

This is a randomized, double-blind, first-in-human (FIH), placebo-controlled single ascending dose (SAD) study to study the safety, tolerability, PK, and PD of EXT608 in healthy adult participants. Each participant will provide written informed consent and must meet all of the eligibility criteria prior to being randomized and administered study product. Participants who discontinue prematurely will be replaced at the discretion of the Sponsor.

##### 3.1.1 Numbers of Cohorts and Participants, and Treatment Allocation

Up to approximately 30 participants may be enrolled to the study intervention such that approximately 24 evaluable participants complete the study.

Additional participants and cohorts may be enrolled pending review of study data and recommendation by a Data Monitoring Board (DMB) and ratification by the Sponsor.

Participants will be enrolled into 1 of up to 6 planned single dose cohorts (designated as S1 through S6, respectively) in ascending fashion.

Each cohort will consist of 4 participants randomized to receive either EXT608 or placebo, whereby 3 will receive a single injection of EXT608 and 1 will receive matching placebo.

##### 3.1.2 Starting Dose

The starting dose will be 4 µg in a volume of 10 ul. Up to 6 dosing cohorts are planned with no single dose escalation to exceed a 3-fold dose increment.

##### 3.1.3 Staggering of Participants after Dose Escalation (Sentinel Participants)

For the first cohort, one participant will be dosed initially. A review of safety data, including Se-Ca and adverse events (AEs) for the first 72 hours post-dose will be conducted by the Investigator and Medical Monitor. If there are no safety concerns, a second participant will be dosed and the same safety review will be conducted to review data up to 72-hrs post-dose. If there are no safety concerns, the last two participants in the cohort will be dosed.

For subsequent cohorts, this staggering requirement only applies to cohorts for doses higher than previously experienced in the study.

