### **Study Design**

This is a randomized, double-blind, first-in-human (FIH), placebo-controlled single ascending dose (SAD) study to study the safety, tolerability, PK, and PD of EXT608 in healthy adult participants. Each participant will provide written informed consent and must meet all of the eligibility criteria prior to being randomized and administered study product. Participants who discontinue prematurely will be replaced at the discretion of the Sponsor.

Participants will be enrolled into 1 of up to 6 planned single dose cohorts (designated as S1 through S6, respectively) in ascending fashion.

Each cohort will consist of 4 participants randomized to receive either EXT608 or placebo, whereby 3 will receive a single injection of EXT608 and 1 will receive matching placebo.

A safe clinical starting dose will be targeted to have a <10% of maximal effect ( $E_{max}$ ) based on allometric scaling of pharmacokinetics (PK) and pharmacodynamics (PD), and will be less than the threshold derived from 1/10 of the human equivalent of the No Adverse Effect Level (NOAEL) established in GLP toxicology studies. Up to 6 dosing cohorts are planned with no single dose escalation to exceed a 3-fold dose increment.

Following a dose escalation, participant dosing for the second and third participant will be staggered at least 72 hours post-dosing pending review of safety data including Se-Ca and adverse events (AEs) by the Investigator and Medical Monitor.

A potential DLT is defined as any of the following EXT608 TEAEs that occurs during the DLT period, graded according to the NCI Common Terminology Criteria for Adverse Events (CTCAE), Version 5.0 (2):

- Grade = 3 TEAE
- Grade = 3 anemia
- Grade = 3 AST/ALT elevation; and/or
- Grade = 2 AST/ALT elevation and Grade = 2 Bilirubin elevation

- Grade = 3 QTc prolongation
- Grade = 3 Hyper- and/or Hypotension
- Grade = 2 Hyperparathyroidism
- Grade = 2 Hyperthyroidism
- Grade = 3 Hypercalcemia
- Grade = 3 Hypocalcemia
- Grade = 3 Hypophosphatemia
- Grade = 3 Hypomagnesemia
- Grade = 3 Creatinine increased

Dose escalation decisions will be based on the NCI Common Terminology Criteria for Adverse Events (CTCAE), Version 5.0 (2) and Se-Ca levels.

The DMB will review the seven-day safety data in each cohort before authorizing the initiation of the next cohort according to the following decision tree:

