### 3.1.5 Dose Escalation

Dose escalation decisions will be based on the NCI Common Terminology Criteria for Adverse Events (CTCAE), Version 5.0 (2) and Se-Ca levels.

The DMB will review the seven-day safety data in each cohort before authorizing the initiation of the next cohort according to the following decision tree:

1. No Grade 3 AEs suspected related to study drug and no indication of effect observed from Se-Ca will result in the next dose at 3x the previous cohort dose.
2. No Grade 3 AEs suspected related to study drug and clear indication of effect on Se-Ca will result in the next dose at 2x the previous cohort dose.
3. A Grade 3 AE suspected related to study drug in a single (n=4) cohort and the absence of prohibitive effects on Se-Ca will result in an additional cohort at the same dose.
4. A single Grade 3 AE suspected related to study drug in 2 cohorts at the same dose (n=8) cohort and the absence of prohibitive indication of effects on Se-Ca will result in a dose escalation to 1.5x the previous dose.
5. Two or more of the same Grade 3 AE within the same cohort suspected related to study drug, or average peak Se-Ca > 1.5 mg/dl above the Upper Limit of Normal (ULN) range will terminate dose escalation.
  - a. If the last dose escalation was 50% and by implication 2 cohorts received the previous dose for an n=8, the study will stop.
  - b. If the last dose escalation was >50%, the next cohort should receive a dose 2/3x the previous dose.

Any DMB recommendation that deviates from the decision tree will be ratified by the Sponsor prior to implementation.

The study schematic is presented in [Section 3.2](#).

[figure not shown]

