## 5.5 Treatment assignment, stratification, and randomization

Treatment allocation is performed in the EDC in a manner that ensures only the unblinded pharmacist or equivalent knows the treatment code.

The treatment assignment is computer generated by the EDC at the point of randomization. Participants are randomized 3:1 active:control in blocks of 4.

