## 7.3 Data Monitoring Board and Dose Escalations

### 7.3.1 Data Monitoring Board

A DMB will be formed to monitor safety and dose cohort choices and provide recommendations to the Sponsor for implementation in the study. The DMB will minimally include an independent Safety Monitor, the Medical Monitor, the Investigator(s), and an independent statistician as voting members, as well as a non-voting coordinator. Operational details will be described in a Safety Plan.

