### 7.3.2 Dose Escalations

When the last participant of a cohort has completed Day 7 and evaluable data are available, statistics will provide a data summary of the cohort data for the DMB. The DMB will meet and decide further actions as described in the Safety Plan.

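### A first branch 5b cohort is exempt from the 72-hour stagger, although its dose is most likely new and 1.33 or 2 times the last dose from which escalation was allowed

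*Protocol*

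**What the plan says.** Section 3.1.3 sets the stagger for cohort 1: one participant, then a second, then the last two, with a 72-hour review by the Investigator and Medical Monitor after each of the first two. For later cohorts it adds: "For subsequent cohorts, this staggering requirement only applies to cohorts for doses higher than previously experienced in the study". The synopsis (Study Design) words the condition differently: "Following a dose escalation, participant dosing for the second and third participant will be staggered at least 72 hours post-dosing".

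Section 3.1.5 gives the decision tree. Branches 1 and 2 step up 3x or 2x when the cohort has had no related Grade 3 event. Branch 3 repeats the dose, and branch 4 steps up 1.5x. Branch 5 ends escalation when one cohort has the same related Grade 3 event at least twice, or when its average peak serum calcium is more than 1.5 mg/dl above the upper limit of normal. Under 5a the study stops if the last step was 50%. Under 5b: "If the last dose escalation was >50%, the next cohort should receive a dose 2/3x the previous dose".

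Every new cohort needs prior authorization: "The DMB will review the seven-day safety data in each cohort before authorizing the initiation of the next cohort". Section 7.3.2 adds: "The DMB will meet and decide further actions as described in the Safety Plan".

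**The concern.** The test in 3.1.3 is whether a dose exceeds the highest given so far. That sensibly exempts a branch 3 repeat, where the exact dose has been given and reviewed. It also exempts a 5b dose, which falls below the highest dose given only because that highest dose met the termination rule.

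The result is uneven. A dose of 2D reached by escalating from D requires 1+1+2 dosing with two 72-hour holds. The same 2D reached through 5b requires none, although the trial then has evidence of a problem at 1.5 times that dose. At stake is how many healthy volunteers receive EXT608 at a new level before anyone has seen 72 hours of data at it.

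**Working it through.** **Inputs.** Cohorts of 4, with 3 on EXT608 and 1 on placebo (3.1.1; also 5.5: "Participants are randomized 3:1 active:control in blocks of 4"). Start 4 µg (3.1.2). Steps 3x, 2x, 1x, 1.5x and 2/3x (3.1.5). No power or sample-size figure bears on the point. The plan's own counts reproduce: 6 × 4 = 24 evaluable participants, and 2 × 4 = 8 at a repeated dose.

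**Which dose 5b refers to.** I read *previous dose* in 5b as the dose just tested, as in branches 1, 2 and 4. The multipliers support this: after a 1.5x step, 1.5 × 2/3 = 1.0, which returns to a dose that already has n = 8, and that explains why 5a stops there. Branch 5a itself, however, uses the phrase for the dose before the escalation. On that reading 5b would give 2/3 × D = 0.67D.

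**Size of a first 5b dose.** Let D be the last dose from which escalation was allowed and k the last step. In the tree, a step above 50% is k = 2 or k = 3. The 5b dose is (2/3)kD:

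- k = 2: 2/3 × 2D = 1.33D. Example: 4, 8 leads to 5.33 µg; 4, 12, 24 leads to 16 µg.
- k = 3: 2/3 × 3D = 2D. Example: 4, 12 leads to 8 µg.

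**Has it been given?** For k = 2 or 3, D < (2/3)kD < kD. Before the last step, D was the highest dose; after it, only kD was added. So the first 5b dose has not been given. It is also below kD, so the 3.1.3 condition is never met. Listing the paths from 4 µg through six cohorts agrees: the 5b dose was already given in 0 of 56 cases, or 0 of 106 if a clean repeat may be followed by 2x or 3x. The inequality already settles this, so the counts add nothing.

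**Exposure before review.** Without a stagger, 3 EXT608 recipients may be dosed before any 72-hour data. With it, the first participant is on EXT608 with probability 3/4, so 0 or 1 recipients are dosed at the first review (mean 0.75) and 1 or 2 at the second (mean 6/4 = 1.5).

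**Illustration on assumed inputs.** Let p be the risk of an event per EXT608 recipient, and q the share of events that show within 72 hours and hold dosing. Neither is in the documents. The chance that two or more recipients have an event is 3p²(1−p) + p³ unstaggered, and p²(1−q)(2−p) + ½p²(1−p)(2−q) staggered, averaging over the placebo position.

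| p | Unstaggered | q = 1 | q = 0.5 | q = 0.25 |
|---|---|---|---|---|
| 1/6 | 7% | 1% | 4% | 6% |
| 1/3 | 26% | 4% | 15% | 20% |
| 1/2 | 50% | 6% | 28% | 39% |

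At p = 1/3, expected events fall from 1.00 to 0.74, 0.87 and 0.93. The model counts any event that would hold dosing and leaves out the calcium trigger.

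**The case against.** The strongest reply is that the scope is deliberate. The title of 3.1.3 and the synopsis both tie sentinels to escalation, and branch 5 ends escalation. A 5b dose lies between two doses that were each given to a full cohort and reviewed to Day 7. The board must authorize the cohort, and its membership is strong: "The DMB will minimally include an independent Safety Monitor, the Medical Monitor, the Investigator(s), and an independent statistician as voting members". Nothing requires simultaneous dosing.

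Much of this stands. The text permits a stagger, and the unsupplied Safety Plan may require one. But the review of the higher dose found the termination rule met. It does not show that two thirds of that dose is tolerated. Board authorization comes before the cohort starts and sees no data at the new level.

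Three stronger inferences are not supported. A reader might take 1.33D and 2D as settled; they depend on the reading of 5b, and at 0.67D the safety argument falls away. A reader might take the table as the benefit to expect; its inputs are assumed, and the gain is small if events appear late, which is possible for an extended half-life product. A reader might also conclude that every dose not yet given needs sentinels. A second consecutive 5b after a 2x step gives 2/3 × 1.33D = 0.89D, below a dose that supported escalation, and the argument here does not reach it.

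**Conclusion.** The gap in the protocol text is real: neither 3.1.3 nor the synopsis requires a stagger in a first 5b cohort. On the likelier reading, that cohort receives a new dose, 1.33 or 2 times D and below a dose that met the termination rule, with up to 3 EXT608 recipients dosed before any 72-hour data at that level rather than 0 or 1.

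The conclusion rests on the reading of 5b given above and applies only if 5b is triggered. The path counts say nothing about how likely that is. Whether there is a gap in practice depends on the Safety Plan. This is a cheap improvement for a first-in-human study in healthy volunteers. It does not show that the plan is unsafe or that it forbids a stagger.

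**What to change.** State in 3.1.3 and the synopsis that the 1+1+2 stagger with 72-hour review also applies to any dose above the highest dose from which the DMB allowed escalation, including a first 2/3x dose under 5b. Keep the exemption for branch 3 repeats and for doses at or below a dose from which escalation was allowed. Add that if dosing is held part-way, the DMB decides whether to complete the cohort, because the tree has no rule for a part-filled one. If the Safety Plan already requires this, a citation in 3.1.3 is enough.

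The cost is one or two sentences and, in a 5b cohort, at least about 6 extra days: 3 + 3 + 7 = 13 days from the first dose to the last participant's Day 7, instead of 7. The cohort may also be held before all four are dosed, with probability 1.5pq − 0.5(pq)². On the same assumed inputs, at p = 1/3 that is 44%, 24% or 12% for q = 1, 0.5 or 0.25, and at p = 1/6 it is 24%, 12% or 6%. Branch 3 and 4 cohorts are unaffected.

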##### 3.1.4 Dose Limiting Toxicity (DLT) Criteria

A potential DLT is defined as any of the following EXT608 TEAEs that occurs during the DLT period, graded according to the NCI Common Terminology Criteria for Adverse Events (CTCAE), Version 5.0 (2):

- Grade = 3 TEAE
- Grade = 3 anemia
- Grade = 3 AST/ALT elevation; and/or
- Grade = 2 AST/ALT elevation and Grade = 2 Bilirubin elevation

- Grade = 3 QTc prolongation
- Grade = 3 Hyper- and/or Hypotension
- Grade = 2 Hyperparathyroidism
- Grade = 2 Hyperthyroidism
- Grade = 3 Hypercalcemia
- Grade = 3 Hypocalcemia
- Grade = 3 Hypophosphatemia
- Grade = 3 Hypomagnesemia
- Grade = 3 Creatinine increased

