1. No Grade 3 AEs suspected related to study drug and no indication of effect observed from Se-Ca will result in the next dose at 3x the previous cohort dose.
2. No Grade 3 AEs suspected related to study drug and clear indication of effect on Se-Ca will result in the next dose at 2x the previous cohort dose.
3. A Grade 3 AE suspected related to study drug in a single (n=4) cohort and the absence of prohibitive effects on Se-Ca will result in an additional cohort at the same dose.
4. A single Grade 3 AE suspected related to study drug in 2 cohorts at the same dose (n=8) cohort and the absence of prohibitive indication of effects on Se-Ca will result in a dose escalation to 1.5x the previous dose.
5. Two or more of the same Grade 3 AE within the same cohort suspected related to study drug, or average peak Se-Ca > 1.5 mg/dl above the Upper Limit of Normal (ULN) range will terminate dose escalation.
  - a. If the last dose escalation was 50% and by implication 2 cohorts received the previous dose for an n=8, the study will stop.
  - b. If the last dose escalation was >50%, the next cohort should receive a dose 2/3x the previous dose.

Any DMB recommendation that deviates from the decision tree will be ratified by the Sponsor prior to implementation.

The study schematic is presented in [Section 3.2](#).

Pending the outcomes of the GLP toxicology and other nonclinical pharmacology studies, planned dose levels will be administered by subcutaneous injection.

A screening visit will take place within 28 days of dosing.

Participants for each cohort will be admitted to the study unit 1 day prior to dosing and remain in the unit through at least 72 hours after dosing for safety and PK assessments before discharge. The total confinement period will be 4 nights, unless extended for management of AEs at the discretion of the Investigator. The schedule of events while inpatient is provided in [Section 7.1.1](#). Follow-up visits to the clinic will occur on/about days 5, 7, 14, 21 and 28. Participants will be monitored closely during the duration of the

study for safety, PK, and PD assessments as described in [Section 3.2](#). The total duration of follow-up period may be modified in the final study design based on safety and PK data from non-clinical studies, anticipated PK/PD response and extended in individual participants as needed to observe their calcium levels return to concentrations deemed not needing further follow up.

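### The escalation tree in Protocol 3.1.5 gives no weight to the potential DLTs that 3.1.4 sets at Grade 2, so a cohort with one still qualifies for a 3x or 2x step

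*Protocol*

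**What the plan says.** Protocol 3.1.4, with the same list in the synopsis under Study Design, gives 13 criteria for a potential DLT. Ten are set at Grade 3. Three are set at Grade 2: hyperparathyroidism, hyperthyroidism, and the combined liver criterion, "Grade = 2 AST/ALT elevation and Grade = 2 Bilirubin elevation".

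Protocol 3.1.5 then gives the decision tree for the next dose:

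- Rule 1: with no related Grade 3 AE, "no indication of effect observed from Se-Ca will result in the next dose at 3x the previous cohort dose".
- Rule 2: with no related Grade 3 AE, "clear indication of effect on Se-Ca will result in the next dose at 2x the previous cohort dose".
- Rule 3: "A Grade 3 AE suspected related to study drug in a single (n=4) cohort", without a prohibitive calcium effect, leads to a further cohort at the same dose.
- Rule 4: "A single Grade 3 AE suspected related to study drug in 2 cohorts at the same dose (n=8) cohort", again without a prohibitive calcium effect, leads to 1.5x.
- Rule 5: escalation ends with two or more of the same related Grade 3 AE in a cohort, or with an average peak calcium more than 1.5 mg/dl above the upper limit of normal.

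The section adds: "Any DMB recommendation that deviates from the decision tree will be ratified by the Sponsor prior to implementation". The synopsis repeats the tree; its first rule opens "No Grade 3 AEs suspected related to study drug and no indication of effect observed from Se-Ca". Section 3.1.2 caps the step: "no single dose escalation to exceed a 3-fold dose increment".

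Section 4.3.1.3 sends potential DLTs to the DMB for evaluation under the Safety Plan. Section 7.3.2 refers to the same plan for the DMB's actions after each cohort.

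**The concern.** The protocol names certain Grade 2 events as potentially dose-limiting, but its rule for choosing the next dose never refers to them. No branch of the tree mentions a DLT or a Grade 2 event. Section 3.3.6 justifies the design as limiting toxicity combined with a pharmacodynamic guide, so the two sections should connect.

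The liver criterion shows the gap best. ALT, AST and total bilirubin are in the safety panel (6.9.3), so the event would be seen, and serum calcium cannot stand in for it. The two endocrine criteria are weaker examples. Section 6.9.3 lists PTH only at screening and no thyroid test. The PD list in 6.9.5 is not visible, although SAP 3.3.3.5 does include serum PTH.

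At stake is the default in a first-in-human study. After an event on the protocol's own list, the written rule can return the largest step allowed, and holding the dose becomes the exception that needs ratification.

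**Working it through.** **Inputs.** Starting dose 4 µg (3.1.2). Cohorts of 4, with 3 active and 1 placebo, and up to 6 cohorts (3.1.1). Multipliers of 3, 2, 1 (repeat) and 1.5 from rules 1 to 4 (3.1.5). As a check on the plan's own count, 6 × 4 = 24, which matches the stated 24 evaluable participants.

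**Applying the tree.** Take a cohort with no related Grade 3 AE and let the number of active participants with a related Grade 2 potential DLT run from 0 to 3.

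| Related Grade 2 potential DLTs | No calcium effect | Clear calcium effect | Average peak calcium above the rule 5 limit |
|---|---|---|---|
| 0 | rule 1, 3x | rule 2, 2x | rule 5, escalation ends |
| 1, 2 or 3 | rule 1, 3x | rule 2, 2x | rule 5, escalation ends |

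The rows are identical, because the number of Grade 2 events is not an input to any rule.

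**Next dose after such an event at 4 µg.**

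- Rule 1: 4 × 3 = 12 µg.
- Rule 2: 4 × 2 = 8 µg.
- Repeat of the dose: 4 × 1 = 4 µg.

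**With the change proposed below.** One or more confirmed events lead to rule 3, so the second cohort receives 4 µg. If the repeat shows no further such event, rule 4 gives 4 × 1.5 = 6 µg. The rule 5 column is unchanged.

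**The equals sign.** The list prints an equals sign before each grade. If this is a greater-than-or-equal sign lost when the PDF was read, the three criteria are still met at Grade 2 and the result is the same.

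**Participants.** One repeat cohort gives 24 + 4 = 28, within the approximately 30 in 3.1.1 and leaving 30 − 28 = 2 for replacements. Two repeats give 24 + 8 = 32, which is above it.

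The documents give no event rates, so no probability is attached to the scenario.

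**The case against.** The best reply is that the list and the tree may have different jobs. Section 3.1.4 defines only a potential DLT, which could be a flag for DMB review, while Grade 3 thresholds set the step. Sections 4.3.1.3 and 7.3.2 hand evaluation and action to the Safety Plan, which was not supplied. The figure at the end of 3.1.5 and the schematic in 3.2 are not shown either. The DMB reviews seven days of safety data before authorizing each cohort and may depart from the tree. Ratification adds little burden, since 7.3.1 already describes the DMB's output as recommendations to the Sponsor. Sentinel review under 3.1.3 asks about any safety concern, without a Grade 3 limit.

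All of this lowers the severity. It does not change the written default: the tree states what each finding leads to, and holding the dose after a related Grade 2 liver event would depart from it. Sentinel dosing limits exposure once the higher dose has been chosen; it does not revise the choice. If the Safety Plan does hold the dose, it and the protocol tree say different things and need aligning.

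Three stronger readings are not supported:

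- A reader might infer that the dose would be tripled automatically after a liver signal. DMB authorization and the deviation clause rule that out.
- A reader might infer that Grade 2 DLTs are handled nowhere. The Safety Plan may cover them.
- A reader might set the dose path after a Grade 2 event beside the path after a Grade 3 AE and quote the ratio as the size of the problem. That compares two different events under the same text, not the present text with amended text.

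Nor should an unblinded DMB be relied on as a safeguard. Protocol 5.4.1 exempts its members from blinding, but SAP 3.5 describes blinded interim summaries for the safety review committee.

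**Conclusion.** The point holds as a mismatch between two sections of the protocol. Three of the 13 potential DLT criteria are set at Grade 2 and have no effect on the tree. Where such an event occurs at the starting dose, the written next dose is 12 or 8 µg instead of a repeat at 4 µg.

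This rests on a cohort with no related Grade 3 AE and no calcium result that triggers rule 5, and on reading the tree as printed. Severity is low to moderate. Confidence is medium, because the Safety Plan and two figures could not be seen. The liver criterion carries the argument; the endocrine criteria add little on the visible text.

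**What to change.** Amend 3.1.5 and the synopsis together:

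- Rules 1 and 2: add *and no event meeting a 3.1.4 DLT criterion that the DMB confirms as suspected related to study drug*.
- Rule 3: add *or one or more such DMB-confirmed events*, leading to a repeat cohort at the same dose.
- Rule 4: count such an event as a Grade 3 AE, so that the step after a repeat with no further such event is 1.5x. Without this, a clean repeat read on its own would return to 3x or 2x.
- Rule 5: leave unchanged, so that two of the same Grade 2 event do not by themselves end escalation.

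Using the same DMB confirmation in each place means that an unconfirmed event still has a branch. Align the Safety Plan with the amended tree, and state there what follows if the repeat cohort shows another such event.

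The edit is short. Its cost is one repeat cohort of 4, and slower escalation, at each dose level where such an event is confirmed. One repeat fits the planned enrolment. A second would exceed it and would need the route in 3.1.1 for extra cohorts: DMB recommendation and Sponsor ratification.
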